3.3 Blinding

Prior to the start of their assigned procedure, patients will be blind-folded and have their hearing damped so that they will be aware of their assigned procedure. It will not be possible to blind the surgical team to treatment given. However, the clinical team involved in patient evaluation post-surgery will have no knowledge of the procedure undertaken by any patients. In addition, the data analyses will be performed with only partially unmasked treatment assignments known to the data analysts (i.e. the analysts will have 'A' / 'B' treatment assignments without knowledge of which procedure corresponds to group 'A' and which to group 'B').

3.4 Study Objectives

The primary objective of this trial is to determine the efficacy of the bariatric arterial embolization (BAE) procedure using radiopaque 100-200 μm microspheres (BTG-001933) for weight loss in obese patients. The secondary objective is to determine the safety of the BAE procedure and use of radiopaque 100-200 μm microspheres in obese patients.

3.5 Outcome Measures

Primary Efficacy Endpoint

The primary outcome is the change in body weight at 12 months' post-procedure from baseline weight.

Secondary Efficacy Endpoints

Secondary efficacy endpoints include the following: 1) Percent change in body weight at 12 months' post-procedure from baseline; 2) The achievement of > 5% reduction in body weight at 12 months' post-procedure; 3) Percent excessive weight loss (EWL) at 12 months' post-procedure from baseline; and 4) Change in MRI biomarkers liver fat proton

density fat fraction (PDFF), visceral adipose tissue volume, subcutaneous adipose tissue volume, and muscle fat infiltration.

Primary Safety Outcome

The total adverse events (AEs) from procedure to 12 months' post-procedure will be used to assess the safety of the BAE procedure and the use of radiopaque 100-200 μm microspheres in obese patients.

Secondary Safety Outcome

The total number of events until day 30 post-procedure will be considered the secondary safety outcome.

Exploratory Outcomes

The following outcomes will be considered as exploratory and potentially supportive of future research studies: 1) Change in blood pressure; 2) Change in lipid/lipoprotein profiles; 3) Change in obesity related hormones (ghrelin, LEAP2, leptin, glucagon-like peptide-1, peptide YY, etc.); 4) Changes in markers of obesity-related complications; 5) Food intake; 6) Hungry and satiety measures; 7) Quality of life as measured by the SF-36 and IWQOL; 8) Endoscopy results; 9) Ghrelin expression in pre- and post-operative fundal biopsy samples; 10) Changes in taste perception; 11) Image analyses of bead distribution and fundal coverage; 12) Embolization endpoints of occlusion and recanalization; 13) Change in muscle volume; 14) Change in muscle fat infiltration; 15) Change in visceral adipose tissue; 16) Change in CHD propensity; 17) Change in DT2 propensity; and 18) Differing treatment response in patients with adverse muscle composition.

3.6 Follow-up

Patient measures will be obtained post-procedure at weeks 1 and 2, and months 1, 3, 6, and 12.

3.7 Pre- and Intra-Procedure Characteristics

Tables of patient summary data will be created for important pre-operative (baseline) characteristics. The variables to be included in this table include: age; race; ethnicity; smoking status; child-bearing potential; comorbidities; and pre-operative weight (in kilograms), body mass index (BMI), percent body fat, excess body weight, diabetic status, blood pressure, laboratory and hematologic variables, and weight circumference.

Additional tables will be created that summarizes intra-operative variables, including procedure time, procedural complications, fluoroscopy time, radiation time, radiation dose, embolic

volume, peri-procedural medications, use of mechanical protection devices, and technical success/failure.

3.8 Power Calculation

Sample sizes per randomized treatment arm for the proposed study are based on providing sufficient power for testing the primary hypothesis that BAE leads to larger mean weight loss from baseline than a sham procedure.

Based on previous data, it is anticipated that the mean weight loss from baseline at 12-months post-randomization in the BAE arm will be at least 8 kg.^{1,2,3} In contrast, we expect that participants in the sham arm will lose 3.3 kg at month 12 post-surgery (corresponding to 3% weight loss from a baseline weight of 110 kg). Also, a common standard deviation for the change in weight from baseline at 12 months of 7 kg is assumed based on the data from the prior BEAT obesity trial. Using a two-sample t-test and a two-sided alpha of 0.2, 21 participants in each arm will provide 80% power. The sample size is increased to 27 participants in each arm (i.e. a total of 54 randomized participants) to take account of an expected 20% drop-out rate by the time of the 12-month assessment. Since this is a phase 2 study, it is appropriate to use a two-sided alpha greater than the standard 0.05 value.

4.0 Analytical Populations

4.1 Full Analysis Set

The Full Analysis Set (FAS) to be used in the analyses of the efficacy outcomes will comprise all study patients who are randomized, undergo and complete the procedure to which they were assigned (embolization or sham surgery), and have at least one post-procedure outcome measure. The FAS will include any multiple imputed values for missing data from these patients.

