9.3 POPULATIONS FOR ANALYSES

Statistical analyses will follow the intent-to-treat paradigm, meaning all participants will be analyzed according to the treatment group to which they were randomized. However, we will also perform an analysis according to a modified intention-to-treat (mITT) paradigm. As defined here, mITT means that all participants will be analyzed based on the treatment arm to which they were randomized, provided that they had exposure to the treatment protocol in their assigned arm. Participants who are randomized to a particular treatment arm, but who do not receive exposure to this treatment will be considered as 'mis-randomized', and will not be included in the mITT population. Reasons for participant mis-randomization include: 1) discovering post-randomization that a given participant does not meet the inclusion / exclusion criteria and is subsequently withdrawn from the study, 2) a participant refuses treatment after randomization, 3) a clinical investigator refuses to treat a participant post-randomization according to the protocol for the treatment arm to which the participant was assigned for any reason, and 4) the participant withdraws from the study post-randomization, but prior to receiving exposure to study treatment, for any reason.

The ten pilot participants recruited in the proposed trial will not be analyzed with the participants recruited through randomization. Rather, these ten pilot participants will be used to test and refine the trial protocol, and data collection procedures.

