1.0 Introduction

This document provides details of the statistical considerations, analyses, and reports planned for the Bariatric Embolization of ArTeries with imaging visibLe EmbolicS (BEATLES) trial. BEATLES is an investigator-initiated, prospective, double-blinded, randomized, sham-controlled study that will assess the impact of bariatric embolization on the systemic levels of obesity-related hormones and, as a consequence, on weight loss. The goal of this study is to help treat obesity combining a lifestyle program and a minimally invasive, angiographic approach.

All data collection procedures and statistical analyses in this SAP report are considered as final, and were finalized and approved by the Clinical Investigators and Sponsor prior to data lock. In addition, the data collection procedures and statistical analyses detailed in this SAP report may modify and are given precedence over the analytical plans outlined in the clinical protocol; however, any major modifications or change in the primary endpoint and/or its analysis will also be reflected in a protocol amendment.

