2.0 CONSORT Diagram

A CONSORT diagram will be created as the trial progresses, and presented at each Data Safety Monitoring Board (DSMB) meeting and at other meetings as requested by the DSMB. This diagram will present a breakdown of patient disposition, and information presented in the figure will include: 1) the number of patients screened; 2) enrolled and randomized numbers; 3) patients who failed screening (along with a breakdown of reasons for trial exclusion); 4) patients removed from the analyses who were enrolled and/or randomized, but found to be ineligible post-randomization; and 5) patients who dropout or were lost-to-follow-up, and reasons for dropping out or lost, if known.

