4.2 Safety Analysis Set

Patients in the Safety Analysis Set (SAS) will include all individuals who are randomized and who underwent the procedure to which they were assigned. Patients in the SAS may include those individuals who do not complete any post-procedure, follow-up visits (i.e. have no post-procedure outcome measures). In addition, patients in the safety data set may include patients who underwent partial embolization or partial sham procedure due to the procedure being stopped short for any reason.

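### The SAP's efficacy set keeps only patients who completed their assigned procedure, while the protocol specifies intent-to-treat and the SAP has no all-randomised set

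*SAP*

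**What the plan says.** **Protocol 9.3** states: "Statistical analyses will follow the intent-to-treat paradigm, meaning all participants will be analyzed according to the treatment group to which they were randomized". It adds a modified intention-to-treat analysis, also as randomised, for participants "provided that they had exposure to the treatment protocol in their assigned arm". That second set asks for exposure. It asks neither for a completed procedure nor for a follow-up measurement.

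**SAP 4.1** defines the Full Analysis Set (FAS) for efficacy as "all study patients who are randomized, undergo and complete the procedure to which they were assigned (embolization or sham surgery") and who have at least one outcome measure after the procedure. On imputation it says: "The FAS will include any multiple imputed values for missing data from these patients".

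**SAP 4.2** (safety set) requires that the assigned procedure was undergone and may include "patients who underwent partial embolization or partial sham procedure due to the procedure being stopped short for any reason". **SAP 4.3** (completer set) requires a completed procedure and all follow-up visits, and serves as a sensitivity analysis to the FAS.

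**SAP 2.0** says the CONSORT diagram will show "patients removed from the analyses who were enrolled and/or randomized, but found to be ineligible post-randomization".

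**SAP 1.0** says the SAP's analyses "are given precedence over the analytical plans outlined in the clinical protocol", but also that "any major modifications or change in the primary endpoint and/or its analysis will also be reflected in a protocol amendment".

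**The concern.** Randomisation makes the arms comparable as randomised. The FAS keeps a patient only if two later things happen: the procedure is completed and an outcome is recorded. The first is decided by a procedural team that, as SAP 3.3 accepts, cannot be blinded. The primary comparison is then conditioned on events after randomisation, which the protocol's own rule avoids.

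The procedures also differ greatly. Under Protocol 6.1.1 the sham is a skin nick with a simulated procedure, while embolisation needs catheterisation and infusion to stasis. It is plausible that incomplete procedures fall mainly in the embolisation arm, but this is an inference: SAP 4.2 foresees partial procedures in both arms.

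Two things are at stake. If excluded patients differ in prognosis and exclusions are unequal between arms, the result can shift in either direction. And if incomplete embolisations bring less weight loss, the FAS estimates the effect of a completed procedure, which is a different quantity from the as-randomised effect. While the documents disagree, the choice between the two populations could also be made after results are known.

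**Working it through.** **1. Who is in which set**

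| Randomised patient | Protocol ITT | Protocol mITT | SAP FAS | SAP safety | SAP completer |
|---|---|---|---|---|---|
| Never underwent the procedure | yes | no | no | no | no |
| Procedure stopped short | yes | yes, if exposed | no | may be | no |
| Completed, no later measure | yes | yes | no | yes | no |
| Completed, some visits missed | yes | yes | yes | yes | no |
| Completed, all visits | yes | yes | yes | yes | yes |

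No SAP column equals the ITT column, and no SAP efficacy set equals the mITT column. Imputation does not close the gap, because SAP 4.1 confines it to FAS members. SAP 5.3 (primary analysis) names no other population.

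**2. The plan's sample size** (Protocol 9.2, SAP 3.8). Expected losses are 8 and 3.3 kg, so the difference is 4.7 kg; SD 7 kg; two-sided alpha 0.20. The two-sample t-test needs 20.41 per arm for 80% power, rounded up to 21, where power is 80.9%. With 20% drop-out, 21/0.8 = 26.25, rounded up to 27. The stated figures reproduce.

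**3. Planned effect present.** The documents give no non-completion rate, so this is an illustration. Suppose k of 27 embolisations are incomplete and those patients lose 3.3 kg, as sham patients do. The FAS still targets 4.70 kg. The as-randomised difference is 4.7 × (1 − k/27). The standard error with 27 per arm is 7 × √(2/27) = 1.905 kg.

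| k | As-randomised (kg) | Gap (kg) | Gap / SE | Power, 21 per arm | Power, 27 per arm |
|---|---|---|---|---|---|
| 0 | 4.70 | 0 | 0 | 80.9% | 87.8% |
| 1 | 4.53 | 0.17 | 0.09 | 78.6% | 85.9% |
| 2 | 4.35 | 0.35 | 0.18 | 76.2% | 83.8% |
| 3 | 4.18 | 0.52 | 0.27 | 73.7% | 81.5% |

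**4. No true effect, exclusions in the embolisation arm only.** Let d be the kilograms by which excluded patients would lose less than retained ones. Dropping k of 27 shifts the arm mean by (k/27) × d; for example, 3/27 × 5 = 0.56 kg. Using the noncentral t with 27 − k against 27, the chance of a false significant result favouring embolisation (nominally 10%) is:

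| k | d = 0 | d = +2.5 | d = +5 | d = −2.5 | d = −5 |
|---|---|---|---|---|---|
| 1 | 10% | 10.9% | 11.8% | 9.2% | 8.4% |
| 2 | 10% | 11.8% | 13.7% | 8.4% | 7.1% |
| 3 | 10% | 12.7% | 15.8% | 7.8% | 5.9% |

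For non-zero d, total two-sided error lies between 0.2005 and 0.2175 against 0.20.

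**5. No true effect, exclusions in both arms with the same d.** The shift is ((k1 − k2)/27) × d. Equal numbers leave the chance at 10%. With 3 against 1 and a 5 kg gap it is 13.7% or 7.1%, depending on the sign of d.

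**The case against.** The wording conflict is not in dispute. The case for treating it as minor runs as follows.

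- **The effect is modest.** This is a phase 2 trial at alpha 0.20. The largest gap above is 0.27 standard errors, and the 15.8% needs three exclusions in one arm plus a 5 kg prognosis gap, larger than the planned effect. With the 21 evaluable per arm the plan expects, these become about 0.24 standard errors and 15%. This stands: no bias has been demonstrated.
- **Few patients may be affected.** Protocol 6.1.1 randomises a sedated, draped patient after eligibility is settled, and a first outcome follows within a week. This partly stands. It does not prevent stopped procedures, and SAP 3.2 instead describes scheduling the procedure after randomisation.
- **The meaning of completion can be inferred.** Protocol 6.1.1 permits treatment of either or both arteries and defines stasis, so one vessel taken to stasis is arguably complete. That is a reasonable reading, but the SAP does not state it.
- **SAP 2.0 only describes a diagram.** True, and SAP 4.1 does not itself exclude an ineligible patient who completed the procedure. But the wording does foresee removal from the analyses.
- **The amendment may be out of view.** The title pages, where the protocol places its current summary of changes, were not available here, and whether this counts as a major change is a judgement. Even so, the current text of Protocol 9.3 says intent-to-treat.
- **An all-randomised set costs something.** Patients never treated may have no later weight and would rest on imputation, and keeping replaced patients takes the total above 54. Both points are right and belong in the wording.

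**Conclusion.** The concern holds. The SAP's efficacy population is narrower than both populations in Protocol 9.3, no SAP set contains all randomised patients, and the precedence clause does not settle the matter because the supplied protocol still specifies intent-to-treat. It should be resolved before data lock because it concerns the primary comparison of a randomised trial and two governing documents give different answers.

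The conclusion rests on that conflict, not on a proven bias. The documents give neither the rate nor the direction of any exclusion. Under the illustrative assumptions (27 per arm, SD 7 kg, up to three incomplete embolisations), the difference in estimate is at most 0.52 kg, and the one-sided false-positive chance ranges from 5.9% to 15.8% around 10%. If exclusion is unrelated to prognosis and there is no true effect, there is no bias.

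**What to change.** **SAP 4.1.** Define the primary efficacy set as all randomised participants, analysed as randomised. State that it includes those found ineligible after randomisation and those replaced under Protocol 7.2. Keep the FAS and completer set as sensitivity sets, say what counts as a completed procedure for the FAS, and report non-completion by arm.

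**SAP 6.0.** Use the observed 12-month weight wherever it exists, including after a stopped procedure; Protocol 7.1 already asks for remaining study procedures to be done after the intervention is discontinued. Impute the rest for all randomised participants. The section promises sensitivity analyses under varied missingness assumptions but specifies no scenarios. One reasonable choice is to impute patients with no procedure or an incomplete one, and no 12-month weight, from the sham arm, because the within-arm model would draw mainly on completed embolisations.

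**Alternative.** If the sponsor prefers the FAS as primary, amend Protocol 9.3 with a justification and report the all-randomised result beside it.

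**Cost.** Wording only, with no extra visits and no change to the planned 54. The as-randomised effect may be smaller: in the illustration, power at 21 evaluable per arm falls from 80.9% to between 78.6% and 73.7%, below the 80% target, but stays at 81.5% or more if all 27 per arm are observed. Good 12-month follow-up is the main protection.

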4.2 Safety Analysis Set

Patients in the Safety Analysis Set (SAS) will include all individuals who are randomized and who underwent the procedure to which they were assigned. Patients in the SAS may include those individuals who do not complete any post-procedure, follow-up visits (i.e. have no post-procedure outcome measures). In addition, patients in the safety data set may include patients who underwent partial embolization or partial sham procedure due to the procedure being stopped short for any reason.

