4.3 Completer Analysis Set

The Completer Analysis Set (CAS) will comprise all patients who were randomized, underwent and completed their assigned procedure, and who completed all post-procedure follow-up

visits (e.g. have at least the primary efficacy measures at post-procedure time points of weeks 1 and 2, and months 1, 3, 6, and 12). Analysis of the treatment effectiveness using CAS will be considered as sensitivity analysis to that performed using the FAS. However, if the efficacy outcome measures are missing completely at random (MCAR) or missing at random (MAR), then estimates of the treatment effect will be unbiased, and should produce results similar to those obtained using the FAS data with multiple imputation (MI) for the missing outcome measures.⁴

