5.4 Analysis of the Safety Measures

The primary safety endpoint will be the differences in adverse events at 12-months post procedure. The statistical analysis on the secondary outcome for safety will consider differences in the adverse events (AEs) at 30-days post-procedure.

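### SAP 4.2 has no as-treated rule: a patient given the other arm's procedure fits no SAP analysis set, and counting a stopped procedure is left optional

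*SAP*

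**What the plan says.** SAP 4.2 defines the Safety Analysis Set as "all individuals who are randomized and who underwent the procedure to which they were assigned". It then widens this in two ways, both worded as permission. Patients with no follow-up visits may be in the set, and the set "may include patients who underwent partial embolization or partial sham procedure due to the procedure being stopped short for any reason". Receipt of the other arm's procedure is not mentioned.

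The other two SAP sets are narrower. The Full Analysis Set (SAP 4.1) takes "all study patients who are randomized, undergo and complete the procedure to which they were assigned", with at least one outcome measured afterwards. The Completer Analysis Set (SAP 4.3) takes "all patients who were randomized, underwent and completed their assigned procedure" and attended every follow-up visit.

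On the purpose of the safety analysis, SAP 3.5 states: "The total adverse events (AEs) from procedure to 12 months' post-procedure will be used to assess the safety of the BAE procedure". On the method, SAP 5.4 states: "The primary safety endpoint will be the differences in adverse events at 12-months post procedure". SAP 5.4 names no analysis set and does not say whether patients are grouped by allocation or by procedure received.

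Protocol 9.3 sets an intent-to-treat principle under which "all participants will be analyzed according to the treatment group to which they were randomized", and a modified version that requires exposure to the assigned arm's treatment. It defines no safety population. SAP 1.0 gives the SAP precedence over the protocol's analysis plans.

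**The concern.** The safety question in this trial is what happens to people who are embolized with an investigational device. That calls for a set defined by exposure. SAP 4.2 instead requires agreement between allocation and receipt, a restriction of the kind used for efficacy sets. Two groups are affected:

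- **Patients given the other arm's procedure.** No SAP definition admits them, so the plan gives no place to report their events in the comparison between arms.
- **Patients whose procedure was stopped.** Permissive wording leaves their inclusion to be decided later, possibly once events are known. A procedure may be stopped because of a complication, so the open choice could bear on the very patients the safety analysis is about. SAP 3.7 expects such cases, since it plans tables of procedural complications and of technical success or failure.

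At stake is whether the primary safety comparison counts everyone who was embolized, in the right column.

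**Working it through.** **The plan's own figure.** The arm size is needed as a denominator, so I checked it first. Inputs from SAP 3.8 and Protocol 9.2: mean loss 8 kg and 3.3 kg (difference 4.7 kg), SD 7 kg, two-sided alpha 0.20, power 80%, dropout 20%.

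- Normal approximation: n = 2 × (1.2816 + 0.8416)² × 7² / 4.7² = 20.0, so 20 per arm.
- Exact noncentral t: power is 79.4% at n = 20 and 80.9% at n = 21, so 21 per arm is right.
- Dropout: 21 / (1 − 0.2) = 26.25, rounded up to 27 per arm, 54 in total.

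The stated sample size reproduces and is not in dispute.

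**Each kind of patient against the three SAP definitions.**

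| Patient | Full set (4.1) | Safety set (4.2) | Completer set (4.3) |
|---|---|---|---|
| Allocated procedure completed | Yes, with at least one later outcome | Yes | Yes, if all visits attended |
| Allocated procedure started, then stopped | No | Optional | No |
| Assigned sham, embolized | No | No | No |
| Assigned embolization, given sham | No | No | No |

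**Would the protocol catch the last two rows?** The modified intent-to-treat set would not, because it requires exposure to the assigned treatment. The intent-to-treat rule would, but by randomized arm, so an unintended embolization would be counted under sham.

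**Illustration A (assumed): one sham-assigned patient is embolized and has the only serious event; all others are treated as allocated.** In fact 28 patients were embolized and 26 had the sham.

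| Basis | Embolization | Sham |
|---|---|---|
| SAP 4.2 as written | 0/27 | 0/26 |
| Protocol 9.3, by randomized arm | 0/27 | 1/27 (3.7%) |
| By procedure received | 1/28 (3.6%) | 0/26 |

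**Illustration B (assumed): one patient assigned embolization receives the sham.** The SAP set holds 26 embolization and 27 sham patients. By procedure received the counts are 26 and 28. No embolized exposure is lost; one sham exposure is.

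**Illustration C (assumed): one embolization is stopped for a complication, which is the only serious event in that arm.** The arm shows 0/26 if the patient is left out and 1/27 (3.7%) if the patient is counted. SAP 4.2 allows either.

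**Range.** The documents give no expected number of wrong-procedure patients. For an assumed k of 1, 2 or 3, the safety set falls from 54 to 53, 52 or 51, a loss of 1.9%, 3.7% or 5.6% of randomized patients.

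**The case against.** The strongest reply is that the wrong-procedure case hardly arises. Under Protocol 6.1.1 randomization takes place on the procedure day after sedation, and the team that sees the allocation carries it out. Embolizing a sham patient would take arterial access, catheter selection and bead infusion by people who know the assignment. This largely stands. SAP 3.2 describes scheduling the procedure after randomization, which leaves somewhat more room for error, but SAP 3.3 confirms that the operators are unblinded either way.

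A second reply is that no safety information is lost. This also stands for data capture. Protocol 8.3.3 requires all on-study adverse events to be documented regardless of relationship, 8.3.5 requires rapid reporting of serious events, and 9.4.6 and 10.1.6 send complication reports to the FDA and DSMB. None of these is the prespecified comparison between arms.

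A third reply is textual. SAP 4.2 says what the set will include, whereas 4.1 and 4.3 say what their sets comprise, so the safety definition may not be exhaustive. The permissive wording on partial procedures may only mean that an incomplete procedure does not disqualify a patient. Both readings are possible. But nothing in the SAP brings in a patient who received the other procedure, and a set definition should not rest on a choice of verb.

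A fourth reply is that grouping by procedure received creates its own ambiguity. Under Protocol 6.1.1 every patient gets local anesthetic and a skin nick, so a patient assigned to embolization who is stopped at that point has had much the same as a sham. This is right, and the remedy needs a rule for it.

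**Conclusion.** The point holds as a gap in the definition. SAP 4.2 has no place for a patient who received the other arm's procedure and no firm rule for a stopped one. The protocol's intent-to-treat rule would not repair this for a safety question.

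The effect depends on events that should be rare. With 27 per arm, one patient can decide whether embolization shows no serious events or one: 0/27 against 1/28 (3.6%) under the assumptions of Illustration A. If every patient completes the allocated procedure, nothing changes.

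A reader might infer three stronger things that the documents do not support:

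- That adverse events would go unrecorded or unreported. The protocol's recording and reporting rules are separate from the SAP's analysis sets.
- That each wrong-procedure patient removes one of 27 embolized exposures. A sham-assigned patient who is embolized is a 28th exposure, of which 27 are counted. In the reverse case no embolized exposure is lost.
- That crossover is to be expected. Neither document gives a number, and the procedure-day arrangements point to few or none.

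This is worth correcting before treatment codes are seen. It does not undermine the trial's design.

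**What to change.** In the SAP:

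1. Redefine 4.2 as all randomized patients in whom any part of either procedure was started, grouped by procedure received.
2. Make inclusion definite, not permissive, both for partial procedures and for patients without follow-up visits.
3. Add a grouping rule for stopped procedures. A patient in whom arterial access for embolization was begun counts as embolization even if no beads were infused. One stopped before that point stays in the assigned arm.
4. Name this set in 5.4 as the population for both the 12-month and the 30-day safety comparisons.

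The cost is a few sentences. Sample size, efficacy sets and data collection are unaffected. The small downside is that the safety groups may differ slightly from the randomized groups. An aggregate summary by assigned arm, shown alongside, makes any difference visible.
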